### 8.3 Reporting Procedure

Per 21CFR312.32(c), all adverse events deemed both serious and unexpected associated with the use of the drug must be reported to the FDA

and to all participating investigators as soon as possible and in no event later than 15 days.

The FDA will be notified of any unexpected fatal or life threatening experience associated with the drug as soon as possible but in no event later than 7 calendar days. The University of Wisconsin Health Sciences-IRB will be notified in accordance with posted institutional policy.

Serious and Non Serious Adverse events will be recorded, regardless of whether or not they are thought to be related to the investigational imaging tracer. While all adverse events will be tabulated and reported in the study final report, serious adverse events will be reported in the course of the trial. Adverse events that meet criteria of a serious adverse event listed above will also be recorded and reported.

The Investigator will inform the IRB of all adverse events attributed to the investigational imaging tracer in accordance with posted institutional policy.

#### 8.4 Additional Adverse Event Information

**CTCAE term (AE description) and grade:** The descriptions and grading scales found in the revised NCI Common Terminology Criteria for Adverse Events (CTCAE) version 5.0 will be utilized for AE reporting. All appropriate treatment areas should have access to a copy of the CTCAE version 5.0. A copy of the CTCAE version 5.0 can be downloaded from the CTEP web site

[http://ctep.cancer.gov/protocolDevelopment/electronic\\_applications/ctc.htm](http://ctep.cancer.gov/protocolDevelopment/electronic_applications/ctc.htm)

To date, no significant adverse events have been reported as a result of the intravenous (IV) administration of FFNP for PET imaging applications (11,12).

As with any IV administered agent, FFNP could cause an allergic reaction that could potentially pose a threat to life (anaphylaxis). This has not been observed in reported human exposure to date. Reasonable precautions should be taken, consistent with normal radiologic and clinical facility practice. The patient should be monitored until the PET procedure is completed, and trained personnel and emergency equipment should be available per facility standards.

For purposes of informed consent regarding reasonably foreseeable risks to subjects in trials utilizing FFNP, the following potential adverse events are considered extremely rare:

- Injection-related risks that may include infection, or accidental extravasation of the dose that may lead to discomfort, localized pain, or infection.

- Risks related to allergic reaction/anaphylaxis that may be life threatening.

As with all PET imaging agents, FFNP is a radiopharmaceutical that decays with positron emission. As such, it poses an intrinsic radiation exposure risk. The organ and total body doses associated with FFNP-PET imaging are comparable to or lower than those associated with other widely used clinical nuclear medicine procedures.

FFNP in combination with other agents could cause an exacerbation of any adverse event currently known to be caused by the other agent, or the combination may result in events never previously associated with either agent.

## **9. MEASURMENT OF TREATMENT OR INTERVENTION EFFECT**

Not applicable since the research imaging studies will not be used to guide therapy.

## **10. STUDY PARAMETERS**

Information regarding time intervals for performance of the study and contact points is included as a table in 5.3.

## **11. DRUG FORMULATION AND PROCUREMENT**

### **11.1 Gadolinium based intravenous contrast agent**

A gadolinium based intravenous contrast agent will be used for the MRI portion of this study. It will be obtained from a commercial source and will be administered following current clinical practice in use at UW Health from breast MR imaging.

### **11.2 21-[18F]Fluoro-16 $\alpha$ ,17 $\alpha$ -[(R)-1'- $\alpha$ -furylmethylidene) dioxyl]-19-norpregn-4-ene-3,20-dione (FFNP)**

FFNP is an investigational new drug which will be used for this study. The radioisotope for FFNP, Fluorine-18, decays by positron emission and has a half-life of 110 minutes. Fluorine-18 is the most frequently used radioisotope for PET radiopharmaceuticals.

#### **11.2.1 Other Names**

[F-18]FFNP, FFNP

#### **11.2.2 Classification**

Investigational new drug: Radiopharmaceutical/radiotracer

### 11.2.3 Mode of Action

FFNP binds to progesterone receptor (PR) with high affinity and selectivity (7-9). In primary and metastatic breast cancer, uptake of FFNP measured by PET/CT imaging has been shown to correlate with PR expression in biopsy material assayed by immunohistochemistry (11). FFNP is primarily cleared from the body via hepatobiliary elimination.

### 11.2.4 Storage and Stability

In accordance with regulations, the facility conducts several quality control tests on the FFNP product prior to release for human administration. Once delivered, doses will be stored in the appropriate storage area in the nuclear medicine facility until they are administered to the patient.

The drug solution is stored at room temperature in a gray butyl septum sealed, sterile, pyrogen-free glass vial with an expiration time of 6 hours.

### 11.2.5 Dose Specifics

The injected dose of FFNP will be approximately 7 mCi (259 MBq) with a specific activity greater than 200 Ci/mmol. Maximum injection dose for a single PET scan will be 10 mCi or less. In all cases, less than 7  $\mu$ g mass dose of FFNP should be injected, which is a subpharmacologic, “tracer” amount.

FFNP is the only active ingredient. There is no evidence that nonradioactive and radioactive FFNP molecules display different biochemical behavior.

### 11.2.6 Preparation

Fluorine-18 labeled FFNP is synthesized with high specific activity so the quantity of progestogenic material injected with the radiopharmaceutical is < 7  $\mu$ g (<16.3 nmol). The final FFNP product solution contains 90% (v:v) USP 0.9% sodium chloride injection and 10% (v:v) USP ethanol alcohol injection. Up to 10 mL of FFNP may be administered for a single PET scan.

Specific manufacturing processes will follow our approved Drug Master File for FFNP.

### 11.2.7 Route of Administration

Intravenous (IV)

### 11.2.8 Incompatibilities

N/A

#### 11.2.9 Availability

cGMP-grade FFNP will be manufactured on-site in the UW-Madison Radiopharmaceutical Production Facility. This facility has been qualified and approved for production by NCI Cancer Imaging Program (CIP) and ECOG-ACRIN for clinical trials using other investigational radiopharmaceuticals, such as  $^{18}\text{F}$ -fluoroestradiol and  $^{18}\text{F}$ -fluorothymidine. The investigational pharmacist or qualified nuclear medicine technologist will be the responsible party designated by the Investigator.

FFNP is not currently commercially available.

#### 11.2.10 Side Effects

See Section 8.4 for side effects. The radiation effective dose equivalent to the whole body from intravenously injected FFNP is estimated to be 0.02 mSv/MBq (11). The dose-limiting organ is the gall bladder, with an average absorbed dose of 0.113 mGy/MBq. The average absorbed dose to the breasts is 0.010 mGy/MBq and the whole-body dose is 0.015 mGy/MBq. The organ and total body doses associated with FFNP PET imaging are comparable to or lower than those associated with other widely used clinical nuclear medicine procedures and are well below the maximum suggested individual study and annual total body dose of 30 and 50 mGy, respectively, suggested for investigational radiopharmaceuticals by the FDA.

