#### 7.1 Administration Schedule

For each research breast imaging session, patients will receive:

- FFNP, approximately 7 mCi (259 MBq), IV slow infusion over approximately 2 minutes followed by saline flush, once
- Gadolinum based intravenous contrast agent, weight-adjusted dose followed by a saline flush, once

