### 16.1.2 PET

There has been one “first-in-human” study involving 20 patients using FFNP PET/CT (11). There were no adverse events, changes in vital signs, laboratory values or electrocardiograms, or clinically detectable pharmacologic effects. Similarly, there were no adverse events or clinically detectable pharmacological effects associated with FFNP administration in

a subsequent phase 2 study involving 43 patients each receiving 2 FFNP PET/CT scans (12).

Risks associated with PET imaging result primarily from the radiation dose from the radiopharmaceutical. For this research study, approximately 7 mCi of FFNP will be administered intravenously which is also the standard dose used for other clinical trials using FFNP (11,12). The radiation effective dose equivalent to the whole body from intravenously injected FFNP is estimated to be 0.02 mSv/MBq (11). Thus for an administered dose of 7 mCi (259 MBq), the whole-body effective dose equivalent is approximately 5 mSv. The dose-limiting organ is the gall bladder, with an average absorbed dose of 0.113 mGy/MBq. The average absorbed dose to the breasts is 0.010 mGy/MBq and the whole-body dose is 0.015 mGy/MBq. Thus for an administered dose of 7 mCi (259 MBq), the whole-body absorbed dose is approximately 3.885 mGy. For context, the average person in the United States receives an estimated effective dose of about 3 mSv per year from naturally occurring radioactive materials, such as radon and radiation from outer space. The current guidance from radiation protection organizations, including American Association of Physicists in Medicine, Health Physics Society, International Organization for Medical Physics, and United Nations Scientific Committee on the Effects of Atomic Radiation (UNSCEAR) states that estimates of risk below levels of about 100 mSv are not statistically different from zero. The organ and total body doses associated with FFNP-PET imaging are comparable to or lower than those associated with other widely used clinical nuclear medicine procedures and are well below the maximum suggested individual study and annual total body dose of 30 and 50 mGy, respectively, suggested for investigational radiopharmaceuticals by the FDA.

16.1.3 CT (performed only in rare instances when the subject is unable to be imaged using the simultaneous PET/MRI scanner).

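### Does the gall-bladder dose contradict the protocol's statement that FFNP doses lie well under 30 and 50 mGy?

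*Combined protocol and SAP*

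**What the plan says.** Section 11.2.10 gives the dosimetry per unit of activity. For the most exposed organ it states: "The dose-limiting organ is the gall bladder, with an average absorbed dose of 0.113 mGy/MBq". Section 16.1.2 repeats that coefficient and adds: "The average absorbed dose to the breasts is 0.010 mGy/MBq and the whole-body dose is 0.015 mGy/MBq". For 7 mCi (259 MBq), Section 16.1.2 multiplies out two quantities. One is an effective dose of about 5 mSv. The other is total-body absorbed dose: "the whole-body absorbed dose is approximately 3.885 mGy".

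Both sections close with the same summary sentence. In Section 11.2.10 its opening words are "The organ and total body doses associated with FFNP PET imaging are comparable to or lower than those associated with other widely used clinical". After naming what is compared, it says that these doses "are well below the maximum suggested individual study and annual total body dose of 30 and 50 mGy, respectively". Section 8.4 makes the comparison with other procedures but leaves out the 30 and 50 mGy figures.

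On activity, Section 7.1 plans about 7 mCi per imaging session, and Section 7.2 allows 3 to 10 mCi. Section 5.8 offers a second scan to up to 5 PR-positive patients, and footnote (j) of Table 2 places it within 14 days of the first.

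Section 11.2.5 also gives a specific activity above 200 Ci/mmol and a mass cap of 7 µg that admits no exception. Section 11.2.6 equates the cap to 16.3 nmol.

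**The concern.** One subject, organ and total-body doses together, governs both halves of the summary sentence. Read as grammar, it asserts that organ doses are far under 30 and 50 mGy. The organ that both sections single out does not fit: its dose is close to 30 mGy for one planned scan, above 30 mGy at the permitted maximum, and above 50 mGy for two planned scans. Neither section multiplies out the gall-bladder coefficient, gives any dose at 10 mCi, or totals the two test-retest scans, so a reader would not notice.

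This is the protocol's summary radiation-safety statement for an investigational tracer. If it misstated a limit that applies to participants, that would matter for oversight of the study, and most of all for the patients injected twice.

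A second question is whether the specific-activity floor is compatible with the mass cap, because a batch exactly at the floor would exceed the cap at the planned activity.

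**Working it through.** **Inputs.** Activity: 7 mCi = 259 MBq (Section 7.1) and a ceiling of 10 mCi = 370 MBq (Section 7.2). Two scans: 518 MBq at 7 mCi each, 740 MBq at 10 mCi each. Coefficients (Sections 11.2.10 and 16.1.2): total body 0.015, breast 0.010 and gall bladder 0.113 mGy/MBq; effective dose 0.02 mSv/MBq.

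**Formula.** Dose = activity × coefficient.

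**The plan's own figures first.**
- Total body at 7 mCi: 259 × 0.015 = 3.885 mGy, as stated.
- Effective dose at 7 mCi: 259 × 0.02 = 5.18 mSv, stated as about 5.
- PET/CT total: 5 + 1.5 = 6.5 mSv, as stated in Section 16.1.3.

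**The same product for each tissue (mGy).**

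| Case | MBq | Total body | Breast | Gall bladder |
|---|---|---|---|---|
| One scan, 7 mCi | 259 | 3.885 | 2.59 | 29.27 |
| One scan, 10 mCi | 370 | 5.55 | 3.70 | 41.81 |
| Two scans, 7 mCi each | 518 | 7.77 | 5.18 | 58.53 |
| Two scans, 10 mCi each | 740 | 11.10 | 7.40 | 83.62 |

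The gall bladder reaches 30 mGy at 30 / 0.113 = 265.5 MBq, or 265.5 / 37 = 7.18 mCi.

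**Which comparison do the reference values support?** The sentence labels 30 and 50 mGy as total-body figures. The like-for-like comparison is the total-body column. It stays under both figures in every permitted case, with a largest entry of 11.10 mGy. The breast column does too. Only the gall-bladder column departs from the literal wording, and there an organ dose is being set against a total-body reference. The documents give no organ reference value, so that column cannot show that anything is exceeded.

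**Specific activity and mass.** The cap implies 7 µg / 16.3 nmol = 0.4294 µg per nmol. At exactly 200 Ci/mmol, 7 mCi is 7 / 200 = 0.035 µmol = 35 nmol, and 35 × 0.4294 = 15.0 µg. The floor alone secures the cap only up to 16.3 nmol × 200 Ci/mmol = 3.26 mCi. But the floor is a minimum and the cap always applies. A batch with higher specific activity meets both conditions, and a dose that met only the floor would not be allowed. The two statements are compatible, and the stricter one governs.

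**The case for a change.** The best case for a change is that a protocol should be judged by what it says. The sentence says organ doses, it appears twice, and it is untrue for the organ both sections call dose-limiting. The planned activity is only approximate, and the gall bladder reaches 30 mGy at 7.18 mCi, just above it. Up to 5 patients receive two injections within 14 days, and no section totals their dose. If only total body was meant, a few words would say so, and the computed gall-bladder doses could be added at almost no cost.

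The arithmetic and the grammatical reading both stand. What does not stand is the inference that the plan needs changing. For one scan at 7 mCi the gall-bladder value is still below 30 mGy, so only the adverb fails. At higher activity, or with two scans, expressing an organ dose as a share of a total-body figure suggests an exceedance that the documents cannot support. The coefficient is printed shortly before the sentence in both sections, so the information is disclosed and a reader needs one multiplication. The effective dose for a planned scan is already given. Consent pages are not in the reviewed copy, so no effect on what participants are told can be shown.

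On mass, the point that the floor does not by itself show how the cap is met is fair but is not an error. Section 11.2.6 refers manufacturing to a Drug Master File outside these documents, and the cap binds whatever that file says.

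**Conclusion.** This is a clerical slip in a descriptive sentence, and correcting it would bring no gain for the trial. The comparison is true for total body by a wide margin: 3.9 mGy for a planned scan, 5.6 mGy at 10 mCi, and at most 11.1 mGy for two scans, against 30 and 50 mGy. As worded it does not hold for the gall bladder (29.3, 41.8 and 58.5 mGy for one 7 mCi scan, one 10 mCi scan and two 7 mCi scans), but no organ limit is stated and no breach is shown. No calculated figure in the protocol is wrong. Following the text exactly as written would change no activity given, no procedure, no sample size, no analysis and no conclusion.

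This rests on the protocol's own coefficients and on reading 30 and 50 mGy as total-body values, which is how they are labelled. The term for the 30 mGy figure, an individual study, is not defined. Whether it means one scan or the whole trial, total-body dose stays under it. Whether a separate organ limit applies cannot be settled from these documents, and none is assumed. The specific-activity floor and the mass cap can be met together, so they need no reconciliation.

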#### 11.2.11 Nursing/Patient Implications

Lactating patients are excluded from this study.

Standard safety precautions required when handling radioactive materials (predominantly during the injection and uptake period) should be followed. FFNP requirements are similar to those used for other PET tracers.

## 12. STATISTICAL CONSIDERATIONS

### 12.1 Primary Objective

12.1.1 To compare FFNP uptake of biopsy-proven primary PR+ breast malignancies measured using PET/MRI with the reference standard of PR immunohistochemistry (IHC).

The primary objective is to compare FFNP  $SUV_{max}$  from PET/MRI with the PR immunohistochemistry semi-quantitative score obtained by using the Allred score (0-8) (1). The correlation of the two measures will be evaluated with Pearson's correlation coefficient. The null hypothesis is  $H_0: p_0=0.20$  and the alternative hypothesis is  $H_1: p_1=0.70$ .

A sample size of 21 patients achieves 80% power to detect this difference, using a two-sided hypothesis test with a Type I error of 5%, accounting for 1 dropout. Sample size calculations were done in PASS 14 (NCSS, LLC, Kaysville, Utah. <http://www.ncss.com>).

Other measures of FFNP uptake including  $SUV_{peak}$  (small fixed-size ROI centered on most metabolically active part of tumor),  $SUV_{mean}$  (average value), tumor-to-normal tissue uptake ratio, and total lesion uptake (functional tumor volume  $\times$   $SUV_{mean}$ ) will also be correlated with the PR immunohistochemistry semi-quantitative score obtained by using the Allred score.

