## STUDY DESIGN

This is a prospective, one-arm, study which will enroll patients with newly diagnosed breast cancer scheduled for diagnostic breast MRI for preoperative staging/extent of disease evaluation as part of standard of care. Eligible patients will be consented for participation in the research study which includes a directed breast PET/MRI with the investigational radiopharmaceutical, FFNP. FFNP uptake of the known, biopsy-proven malignancy will be measured using standardized uptake values (SUV) and tumor-to-normal tissue ratios. The proposed work-flow is described in the schema below.

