### 5.5.6 Research Imaging Analysis

Two independent readers blinded to the clinical outcome will undergo two sessions of image interpretation of FFNP-PET/MRI scans separated in time by a washout period of at least 4 weeks. Images will be reviewed for general quality. The known biopsy-proven breast cancer(s) will be identified on the PET/MRI examinations based on its known location from the prior clinical breast MRI, if performed, or the patient's previous imaging, as is typically done in routine clinical practice. MRI will be used to localize the lesion(s), measure the lesion size (in three dimensions), and assign the region of interest (ROI) for PET imaging analysis. Each lesion will be analyzed for (1) qualitative appearance (visible above background or not) and (2) semi-quantitative FFNP uptake.

**Qualitative Analysis of FFNP uptake (lesion-level):** FFNP uptake will be evaluated qualitatively with the following grading scale: no uptake (tumor < background), minimal uptake (tumor = background), mild (tumor slightly > background), moderate uptake (tumor >> background), and intense uptake (tumor >>> background). Tumor uptake will also be dichotomized as increased (moderate or intense uptake) or absent (no uptake, minimal or mild uptake).

**Quantitative Analysis of FFNP uptake (lesion-level):** Standardized uptake values (SUV) will be measured by manually drawing a region of interest (ROI) to encompass the entire lesion guided by the lesion extent visualized on anatomic imaging. SUV analyses will include, but not be limited to,  $SUV_{\max}$  (maximum value),  $SUV_{\text{peak}}$  (small fixed-size ROI centered on most intense part of tumor),  $SUV_{\text{mean}}$  (average value), and  $SUV_{\text{sd}}$  (standard deviation). Tumor-to-normal tissue uptake ratios will also be measured. Other PET imaging parameters will include FTV (functional tumor volume; i.e. the volume of tumor tissue with increased FFNP uptake) and TLU (total lesion uptake; i.e. the product of  $FTV \times SUV_{\text{mean}}$ ). Within lesion heterogeneity will be explored using the method described by Kurland et al (16).

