## 12.2 Secondary Objectives

- 12.2.1 To determine the test-retest reproducibility of quantitative assessment of tumor FFNP uptake.

The reproducibility of the two measurements of FFNP uptake will be evaluated in the 5 subjects who elect to undergo a second imaging session, using summary statistics of tumor FFNP uptake for each reading for PET/MRI. The analysis will be done separately for each reader.

- 12.2.2 To determine the intra- and inter-observer variability of quantitative assessment of FFNP.

The intra- and inter-reader agreement of SUV values for tumor FFNP uptake will be analyzed with Bland-Altman plots and 95% limits of agreement. Analyses will be conducted on a per-lesion basis, and repeat tumors within the same patient will be assumed to be independent.

- 12.2.3 To evaluate the optimal cut-point of FFNP uptake for distinguishing between PR negative and PR positive invasive breast cancer.

Receiver operating characteristic (ROC) curve analysis will be performed to determine the optimal cut-point for FFNP uptake to distinguish PR-positive from PR-negative invasive breast cancer, as

defined by the clinical pathology report. The area under the curve for the ROCs and their respective two-sided 95% confidence intervals will be calculated using logistic regression. The optimal cut-off point will be determined by considering the FFNP uptake value with the maximum sensitivity and specificity. The analysis will be done separately for each reader.

- 12.2.4 To estimate the association of tumor FFNP uptake (continuous SUVmax) with research-based Oncotype DX scores (0-100).

Scatter plots of continuous FFNP uptake (SUVmax) on the y-axis and research-based Oncotype DX scores (unitless) on the x-axis will be created to explore the distribution of the measurements. Pearson's or Spearman's rank correlation will be used to evaluate the association between FFNP uptake and research-based Oncotype DX score. The correlation coefficient (rho) and 95% confidence interval will be reported.

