### 12.3 Exploratory Objectives

- 12.3.1 To evaluate heterogeneity of tumor FFNP uptake.

The coefficient of variation (COV), defined as standard deviation of the standardized uptake value (SUV) and the mean value of the SUV will be assessed. Other descriptive measures such as skewness and kurtosis, which are measures of asymmetry and heaviness of the tails, relative to the normal distribution will be assessed. The analysis will be done separately for each reader.

- 12.3.2 To correlate tumor FFNP uptake with serum progesterone and estradiol levels.

A correlation analysis of serum progesterone and estradiol levels with tumor FFNP uptake measured with SUV values will be performed using Pearson's or Spearman's rank correlation. Scatter plots, correlation coefficients (rho), 95% confidence intervals, and p values will be reported. This analysis will be done separately for each reader.

- 12.3.3 To correlate tumor FFNP uptake with disease recurrence.

If there is sufficient follow-up data for disease recurrence, the Kaplan-Meier method will be used to analyze time to disease recurrence, defined as date of imaging day until disease recurrence.

Patients who do not experience disease recurrence will be censored at the date of last available follow-up. A Cox proportional hazards model will be used to evaluate the association of tumor FFNP uptake with time to disease recurrence. If there is insufficient follow-up data, descriptive statistics will be used to summarize the tumor FFNP uptake for those patients with disease recurrence.

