#### **13.2 Required Pathology Materials**

Pathology reports will be available through the electronic medical record. Existing pathology slides (PR IHC and H&E) from the breast biopsy used for initial diagnosis will be requested from the Department of Pathology for semi-quantitative Allred scoring by the research study pathologist if the information needed to calculate the Allred score is not included in the clinical pathology report.

For the research-based Oncotype DX score, a study pathologist will review the H&E slides from the surgical specimen and select a block for release to

the TRIP Laboratory. We anticipate needing 6 unstained sections per patient specimen for sufficient RNA isolation for the assay.

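### Does the primary correlation need a written rule for which tumour counts when a patient has more than one?

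*Combined protocol and SAP*

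**What the plan says.** Section 12.1.1 sets the primary analysis as "The correlation of the two measures will be evaluated with Pearson's correlation coefficient", with a null value of 0.20 and an alternative of 0.70. It sizes the test in patients: "A sample size of 21 patients achieves 80% power to detect this difference", one of the 21 being a dropout allowance.

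Uptake is a lesion measurement. Section 5.5.6 states "The known biopsy-proven breast cancer(s) will be identified on the PET/MRI examinations" and "Each lesion will be analyzed for (1) qualitative appearance (visible above background or not) and (2) semi-quantitative FFNP uptake". The Protocol Summary, under Study Design, uses the singular: "FFNP uptake of the known, biopsy-proven malignancy will be measured using standardized uptake values".

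The only rule for several tumours in one patient is in Section 12.2.2, on reader agreement: "Analyses will be conducted on a per-lesion basis, and repeat tumors within the same patient will be assumed to be independent".

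Two later analyses pair lesion uptake with a value obtained once per patient. For the Oncotype DX score (12.2.4), Section 13.2 says "a study pathologist will review the H&E slides from the surgical specimen and select a block for release to" the laboratory. For the hormone correlation (12.3.2), one blood sample is drawn before injection (Section 5.6), and "Scatter plots, correlation coefficients (rho), 95% confidence intervals, and p values will be reported".

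**The concern.** The test is sized in patients and the measurement is per lesion, and nothing in 12.1.1 connects the two. Eligibility does not exclude multifocal disease, and patients are recruited around MRI done to assess extent of disease, so a second biopsy-proven tumour is plausible. With about 20 points, one or two values can move a correlation across the threshold. If the tumour were picked after SUVmax and the Allred scores had been put together, the picker could influence the primary result. If all tumours were entered as though independent, as 12.2.2 does for reader agreement, error would be somewhat above nominal. In 12.2.4, the tissue block and the SUVmax could also come from different tumours.

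**Working it through.** **1. The plan's own figure.** Inputs from 12.1.1: correlations 0.20 and 0.70, two-sided 5%, 21 patients less 1 dropout = 20.

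- Fisher z: atanh(0.70) − atanh(0.20) = 0.8673 − 0.2027 = 0.6646. Times √(20 − 3) = 4.123 gives 2.740. Less 1.960 gives 0.780, so power is 78.2%.
- Exact distribution of r under bivariate normality: critical r 0.595, power 80.2% at n = 20 and 77.9% at n = 19.

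The exact two-sided calculation therefore gives 20 + 1 = 21. (The Protocol Summary calls the test one-sided, which would give 88.0% at n = 20. That is a separate matter.) The figure stands on one pair of values per patient.

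**2. What the text implies.** The sizing unit is the patient, and Study Design speaks of a single known malignancy. When the pathology report lacks the details for an Allred score, Section 13.2 requests slides from the biopsy that made the initial diagnosis. All three lead to one tumour per patient, the one first diagnosed. The independence sentence in 12.2.2 belongs to the reader-agreement analysis and is not carried into 12.1.1.

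**3. How much the choice matters.** No document gives the number of patients with two tumours or how alike two tumours in one patient are. Both are assumed.

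- Model per tumour: value = √ICC × patient effect + √(1 − ICC) × lesion effect, for SUVmax and Allred, with lesion-level correlation ρ. ICC is the within-patient (intraclass) correlation, taken as 0.3-0.8 for SUVmax and 0.3-1.0 for Allred.
- Test: Fisher z against 0.20, n = 20. Reject upward if r > tanh(0.2027 + 1.960/4.123) = tanh(0.678) = 0.590.
- 40,000-100,000 simulated trials per setting.

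Results with 2 of 20 patients having two tumours:

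| | ρ = 0.70 | ρ = 0.20 |
|---|---|---|
| Some choice significant, another not | 6.4-12.3% | 1.2-2.9% |
| Largest and hottest tumour disagree | 2.9-5.3% | not run |
| Success, fixed one-tumour rule | 80.5-81.4% | 2.5-2.8% (upper side) |
| Success, most favourable tumour picked | 84-87% | 3.3-4.2% (upper side) |
| Both tumours entered as independent | 83-85% | 5.2-6.3% (two-sided) |

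The ρ = 0.20 entry in the first row comes from a run with ICC from 0 to 0.9. That run gave 12.7% (ICC 0) to 5.6% (ICC 0.9) at ρ = 0.70.

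With 1 such patient, the first row at ρ = 0.70 is 3.1-6.3% and the second 1.6-3.1%. With 4 they are 12.6-24.4% and 4.5-8.7%.

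**4. Reading the table.** Two valid rules that disagree in 3-5% of trials are not in error. Each has the planned power and error, and they differ only because they draw a different tumour from the same patient. Only the last two rows show harm. Picking the favourable tumour adds at most about 4.2 − 2.7 = 1.5 percentage points of false success. Entering both adds at most 6.3 − 5.0 = 1.3 points of two-sided error.

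**5. The other analyses.** These figures assume 25 patients (20 PR-positive plus up to 5 PR-negative), two of them with two tumours and both tumours entered. The Oncotype DX 95% interval then covers 93.8-94.5%, and the 5% hormone test rejects in 5.4-6.3%. The 25 is an upper bound for Oncotype DX, because the assay needs leftover tissue.

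**The case for a change.** The best argument for a change is that the rule costs a few sentences and no patients, and that without it a reader of the results cannot tell whether the tumour was named before or after the data were seen. The singular wording in Study Design gives no answer for a patient with two tumours. The slide request in 13.2 is only a fallback, and it does not settle two tumours biopsied at diagnosis. The readers are blinded to clinical outcome, which does not fix the lesion. The 6-12% also depends on the model: a six-level Allred score (3-8, with an assumed spread) gives 7.7-14.8%, and a single Allred score shared by both tumours gives 4.9-23.0% across ICC values.

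The silence is conceded, and so is the value of naming the tumour early. But the larger percentages count every possible choice, at a true correlation of 0.70, for an assumed number of patients. They describe how far the result could be moved by someone set on moving it. The affected group is also narrow. The primary objective is limited to PR-positive tumours, so a patient must have two biopsy-proven, PR-positive tumours, each with uptake and an Allred score. Sections 5.1, 5.4 and 5.5.1 prefer, and Section 6 requires, research imaging before biopsies prompted by the clinical MRI. A lesion found that way would often not yet be a known cancer at the scan, although it could be proven by the time of analysis.

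**Conclusion.** No change follows. Section 12.1.1 leaves out a detail; it states no wrong number and no wrong rule. The patient-based sample size reproduces, the surrounding text points to one tumour per patient, and any natural rule fixed beforehand keeps power at about 81% and upper-side error at 2.5-2.8%. An analyst would make that choice without being told. The damaging alternatives, choosing after the fact or treating two tumours as independent, are not prescribed for the primary analysis. With an assumed two such patients, either would raise the error rate by at most about 1.5 percentage points. The effects on 12.2.4 and 12.3.2 are of similar size and concern a secondary and an exploratory analysis.

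This rests on assumed numbers of two-tumour patients (1, 2 or 4 of 20), an assumed within-patient correlation and a normal model. If many more patients had two PR-positive tumours, the choice would carry more weight. If none do, the question does not arise.
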